## 7.2 Study Conduct

Relevant protocol deviations are summarized by treatment regimen for treated subjects. Relevant protocol deviations are those that could potentially affect the interpretability of the study results. A list of programmable relevant protocol deviations is provided in [Appendix 1](#), including:

- Eligibility deviations (based on deviations of subject inclusion and exclusion criteria from Protocol Sections 4.2.1 and 4.2.2 which can be programmed from the database) during the pre-treatment period. If multiple measurements are available, a subject is considered to have a deviation only if all measurements fail the inclusion or exclusion criterion, except for pregnancy.
- Deviations during the on-treatment period (eg, incorrect dosing received).
- Deviations related to PK data.

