4.2.1 Inclusion Criteria

1) Signed Written Informed Consent

- a) Freely given informed consent must be obtained prior to clinical trial participation, including informed consent for any screening procedures conducted to establish subject eligibility for the trial. Minor's parents or legally acceptable representatives must give fully informed written consent. Assent should be obtained when the minor is judged to be of an age of reason (see [Appendix 1](#));

2) Target Population

- a) History of CHB infection defined as HBsAg-positive at the Screening visit and on at least one other occasion ≥ 24 weeks prior to screening;
- b) Detectable HBeAg AND no detectable anti-HBe antibodies at screening and at least once ≥ 4 weeks prior to screening;
- c) Serum ALT 1.5 to $< 10 \times$ ULN at screening and at least on one other occasion within 8 to 24 weeks prior to screening;
- d) HBV DNA by PCR $\geq 10^5$ copies/mL at screening and evidence of the presence of HBV DNA at least once ≥ 4 weeks prior to screening;

3) Age and Sex

- a) Male and females, 2 to < 18 years of age.

Women of childbearing potential (WOCBP) must be using an adequate method of contraception to avoid pregnancy throughout the study and for up to 6 weeks after the last dose of investigational product in such a manner that the risk of pregnancy is minimized.

WOCBP include any female who has experienced menarche and who has not undergone successful surgical sterilization (hysterectomy, bilateral tubal ligation,

or bilateral oophorectomy) or is not postmenopausal. Post menopause is defined as:

- Amenorrhea \geq 12 consecutive months without another cause or
- For women with irregular menstrual periods and on hormone replacement therapy (HRT), a documented serum follicle stimulating hormone (FSH) level $>$ 35 mIU/mL

Women who are using oral contraceptives, other hormonal contraceptives (vaginal products, skin patches, or implanted or injectable products), or mechanical products such as an intrauterine device or barrier methods (diaphragm, condoms, spermicides) to prevent pregnancy, or are practicing abstinence or where their partner is sterile (eg, vasectomy) should be considered to be of childbearing potential.

WOCBP must have a negative serum or urine pregnancy test (minimum sensitivity 25 IU/L or equivalent units of HCG) at screening AND within 72 hours prior to the start of investigational product.

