- a) ≥ 12 weeks of prior therapy with any nucleoside or nucleotide antiviral agent with activity against hepatitis B virus (including but not limited to adefovir, tenofovir, famciclovir, clevudine, lamivudine, telbivudine, or emtricitabine);
- b) Therapy with interferon alpha, thymosin alpha or any nucleos[t]ide antiviral agent with activity against hepatitis B virus within 24 weeks of screening;
- c) Any prior therapy with ETV;
- d) Any use of illegal drugs OR use of alcoholic beverages which in the investigator's opinion is sufficient to prevent adequate compliance with study procedures or increase the risk pancreatitis or hepatotoxicity;
- e) Concomitant medications which may cause immunosuppression, nephrotoxicity or hepatotoxicity or affect renal excretion or hepatic metabolism are not permitted;

- f) Concomitant use of Traditional Chinese Medicines or other herbal products purported to have antiviral activity or intended for use in improving/protecting liver function;
- g) During the treatment phase of the study, a subject may not be coenrolled in another clinical trial where an investigational drug is administered;

7) Other Exclusion Criteria

- a) Unable to tolerate oral medication;
- b) Children that are currently breastfeeding, or those who were breastfed while their mother received LVD; maternal LVD treatment during pregnancy;
- c) Prisoners or subjects who are involuntarily incarcerated;
- d) Subjects who are compulsorily detained for treatment of either a psychiatric or physical (eg, infectious disease) illness.

A liver biopsy prior to the start of study medication is optional. If a biopsy has been performed prior to randomization, then histological results will be collected; likewise, results from any subsequent on-study biopsies will be collected.

Subjects may be rescreened twice (for a total of three screens) if it can be reasonably expected that study criteria will be met. However, beyond this, subjects should be reevaluated only after consultation with the study team.

Eligibility criteria for this study have been carefully considered to ensure the safety of the study subjects and to ensure that the results of the study can be used. It is imperative that subjects fully meet all eligibility criteria.

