## 6 STUDY PERIODS, TREATMENT REGIMENS AND POPULATIONS FOR ANALYSES

### 6.1 Study Periods

Study periods for efficacy and safety analyses are defined as follows:

- **Pre-treatment period** begins at the first visit until initiation of study therapy.
- **On-treatment period** begins after the first day of study therapy and ends at the last dose of study therapy plus 5 days.
- **ETV treatment period** begins after the first day of active ETV and ends at the last dose of active ETV plus 5 days.
- **Off-treatment follow-up period** begins on the last dose of study therapy plus 6 days and ends at the start of alternative anti-HBV therapy minus 1 day.
- **Long-term follow-up period** begins on the last dose of study therapy plus 6 days until the end of the study.
- **Alternative ETV follow-up period** begins on the later of the last dose of study therapy plus 6 days and the start of alternative ETV therapy, until the end of the study.

Note that rescue open-label ETV is considered alternative anti-HBV therapy. See [Section 8.9](#) for additional conventions.

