### Eligibility Deviations

Eligibility deviations (ie, protocol deviations of entry criteria) are listed below.

- Inclusion 2b: HBeAg negative or missing, or HBeAb positive or missing at screening
- Inclusion 2c: ALT < 1.5 x ULN or  $\geq 10 \times$  ULN or missing at screening
- Inclusion 2d: HBV DNA <  $10^5$  c/mL or missing at screening
- Inclusion 3a: Age < 2 or  $\geq 18$  years
- Exclusion 1d: Women with positive pregnancy test at screening
- Exclusion 2a: Positive test for HIV, HCV or HDV at screening.
  - HCV positive is defined as both HCV antibody positive and detectable HCV RNA.
  - HIV positive is defined as having a positive result for HIV-1 and HIV-2 screen and either HIV-1 confirmation or the HIV-2 confirmation immunoblot.
- Exclusion 4a: Hemoglobin < 10.0 g/dL or missing at screening
- Exclusion 4b: Platelets count <  $70,000/\text{mm}^3$  or missing at screening
- Exclusion 4c: Glomerular filtration rate < 50 mL/min/1.73 m^2 or missing at screening. This is estimated using Schwartz formula.
- Exclusion 4d: Total bilirubin > 2.5 mg/dL (> 42.75  $\mu\text{mol/L}$ ) or missing at screening
- Exclusion 4e: INR > 1.5 or missing at screening
- Exclusion 4f: Albumin < 3 g/dL (< 30 g/L) or missing at screening
- Exclusion 4 g: Alpha fetoprotein  $\geq 50$  ng/mL or missing at screening
- Exclusion 6a: Prior therapy  $\geq 12$  weeks with any anti-HBV nucleoside or nucleotide. This includes, but is not limited to adefovir, tenofovir, famciclovir, clevudine, lamivudine, telbivudine or emtricitabine (#)
- Exclusion 6b: Prior therapy with interferon alpha, thymosin alpha or any anti-HBV nucleos[t]ide antiviral agent within 24 weeks of screening (#)
- Exclusion 6c: Prior ETV

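### SAP 7.2 lets any one passing pre-treatment result clear an eligibility deviation, although the protocol requires the qualifying screening result itself to pass

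*SAP*

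**What the plan says.** SAP 7.2 summarises relevant protocol deviations for treated subjects and describes them as those that could affect how the results are interpreted. Eligibility deviations are those "which can be programmed from the database) during the pre-treatment period". The rule for repeat results opens with "If multiple measurements are available" and continues: "a subject is considered to have a deviation only if all measurements fail the inclusion or exclusion criterion, except for pregnancy". SAP 6.1 defines the pre-treatment period as one that "begins at the first visit until initiation of study therapy".

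SAP Appendix 1 lists the programmed checks. Nearly all the laboratory checks refer to the value at screening, and most also count a missing value as a deviation.

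Protocol 4.2.1 requires ALT of 1.5 to < 10 x ULN "at screening and at least on one other occasion within 8 to 24 weeks prior to screening". Criterion 2b has the same two-part form, and 2d requires the HBV DNA threshold at screening plus earlier evidence of HBV DNA. Protocol 4.2.2 allows two rescreens and adds: "It is imperative that subjects fully meet all eligibility criteria".

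**The concern.** The two rules run in opposite logical directions. Under the protocol, one failing required result makes a child ineligible. Under SAP 7.2, one passing result makes the child compliant. Take a child with ALT 1.2 x ULN at the qualifying screen and 1.6 x ULN on Day 1. That child breaches criterion 2c, yet would not appear in the table if the Day 1 value is pooled.

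The credibility of the deviation table is at stake. Amendment 2 raised the ALT threshold from 1.3 to 1.5 x ULN and lengthened the minimum interval between the two ALT measurements from 4 to 8 weeks. A reader would look to this table to see whether those conditions were met in each arm. If breaches are netted off against other results, the randomised children look closer to the entry criteria than they were.

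**Working it through.** **1. Can several results exist?** Yes, by design. Protocol Table 6.1 schedules chemistry and hematology, INR, hepatitis B serology and HBV DNA both at screening and in the randomisation/Day 1 column. The SAP pre-treatment period runs to the start of therapy, so it can hold both results, plus any from earlier screens.

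**2. Do the SAP passages agree on which results count?** No.
- SAP 7.2 with SAP 6.1: any result from first visit to first dose.
- SAP Appendix 1: the value at screening. This may exclude Day 1, but does not say which screen counts when there are several.

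Two programmers could build different tables. On the narrower reading Day 1 drops out, but a passing value from an earlier screen that failed on another criterion would still cancel a failing value at the qualifying screen.

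**3. The earlier supporting values.** Appendix 1 programs only the screening part of 2b, 2c and 2d. A failed or absent earlier value is uncounted for that reason as well, whatever 7.2 says.

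**4. Size, in general form.** The plan gives no figure to reproduce. Let c be the probability that a second result fails given that the first failed.
- Screening result required, one other result pooled in: share of breaches missed = 1 - c. This is 95% at c = 0.05, 50% at c = 0.5, 20% at c = 0.8 and 0% at c = 1.
- Two results both required, with equal failure rate q: P(any failure) = q(2 - c) and P(both fail) = qc, so share missed = 1 - c/(2 - c) = (2 - 2c)/(2 - c). This is 97% at c = 0.05, 67% at c = 0.5, 33% at c = 0.8 and 0% at c = 1.
- Only one screening result available: 0% missed.

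The documents give no value for c.

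**5. Size for ALT, by simulation.** All inputs are assumptions: log-normal ALT, median 2-3 x ULN, between-child log-SD 0.5, within-child log-SD 0.2-0.5, 2 million children per setting. A breach is a screening ALT < 1.5 x ULN. It is cleared if a further pre-treatment ALT lies in 1.5 to < 10 x ULN.

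| Breaches considered | Cleared by one further ALT |
|---|---|
| Historical ALT valid | 55-69% |
| Any historical ALT | 25-60% |
| Historical ALT also failing | 15-46% |

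With two further ALTs and a valid historical value, 73-87% are cleared, but the second extra ALT would have to come from a rescreen or retest because the visit schedule does not supply it. The 55-69% row corresponds to c of 0.31-0.45. It is high because children with a valid historical ALT who then fall below the limit tend to sit close to it.

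**The case against.** The strongest reply is that Appendix 1 ties the checks to screening, so in the ordinary case of one screening value the rule in 7.2 never operates and every failure is flagged. Where there were several screens, ignoring a failed first screen followed by a passing one is correct, because the protocol permits rescreening. Both points stand. What remains is that 7.2 and 6.1 point to a wider window than Appendix 1, and that the rule also works in reverse, letting an earlier pass excuse a later failure at the screen that led to randomisation.

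A reader might infer that most real breaches vanish. The documents do not support that. The simulated share exceeds one half throughout only for ALT, only if a further value is pooled, and only given a valid historical ALT. Age and prior-therapy criteria are not repeated laboratory values at all. The simulation also treats every child with a failing screening ALT as randomised, whereas most should be screen failures (Protocol 8.1 plans for about 30%).

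A reader might also infer that co-infected children would be cleared under "Positive test for HIV, HCV or HDV at screening". Before treatment these serologies are scheduled at screening only, so there is no Day 1 value to cancel a positive, and Appendix 1 already defines confirmation for HIV and HCV. Discordant results would need a retest or rescreen, and no separate rule is warranted.

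Finally, the table is not the only record. SAP 7.3.4 summarises baseline ALT, HBeAg, anti-HBe and HBV DNA, Protocol 9.1.1 requires significant deviations to be documented in the CRF, and the Appendix 1 list may be extended from monitoring. That limits the harm. Baseline summaries, however, use the last value before dosing, and so do not show whether the screening criterion was met.

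**Conclusion.** The concern holds in limited form. As written, SAP 7.2 can remove a true eligibility breach from the relevant-deviation table whenever a Day 1 or earlier-screen result is pooled with the qualifying one, and the SAP does not settle whether it is. For ALT, one further value clears about 25-69% of screening breaches under the assumptions above; the range reflects the assumed ALT distribution and whether the historical ALT is required to be valid. The number of children affected cannot be derived from the documents.

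The consequence is an understated count of ineligible children in a descriptive table. A reader might infer that the primary result is at risk. It is not: SAP 7.5 analyses treated subjects as randomised, and SAP 6.3 defines no set that excludes deviators, so no estimate, interval or p-value changes.

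**What to change.** In SAP 7.2, replace the all-must-fail sentence with wording such as:

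> *Each programmable criterion is assessed on the qualifying (final) screening result used for randomisation. Results from earlier screens and from Day 1 do not cancel a failing result. The exception for pregnancy is retained.*

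Use the same definition of the qualifying result in Appendix 1, so that the two places cannot be programmed differently. A permitted rescreen that passes then remains correctly uncounted.

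Separately, either program the earlier-value parts of 2b, 2c and 2d where the data are held, or state in Appendix 1 that they are checked by monitoring.

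The cost is a few lines of SAP text and a programming change, with no new data collection for the screening-value check. The downside is a somewhat higher reported deviation count.

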## 7.3 Study Population

### 7.3.1 *Pre-Randomization Subject Status and Accrual Pattern*

Pre-randomization subject status is summarized for enrolled subjects. This presents the number of subjects enrolled, randomized and not randomized. Reasons for not randomized are also included (eg, AE, death, lost to follow-up).

The numbers of subjects enrolled and randomized are summarized by site for each country.

Enrollment by age group is summarized analogously. Age groups are: in utero; preterm newborn (gestational age < 37 weeks); newborns (0 to 27 days); infants and toddlers (28 days to 23 months); children (2 to 11 years); adolescents (12 to 17 years); adults (18 to 64 years); adults (65 to 84 years); adults ( $\geq$  85 years).

### 7.3.2 *Accounting for Patient Identification Number (PID) Assignments*

PIDs assigned by the RIVRS randomization system at enrollment are listed in an Appendix to the study report.

### **7.3.3 Subject Disposition**

Summaries are presented by as-treated treatment regimen unless specified otherwise.

Subject disposition from the start to end of treatment is based on the end of treatment subject status CRF, and varies according to the analysis (see [Section 9](#)): the number of subjects treated, discontinued before Week 48, discontinued at Week 48 or before Week 96, discontinued at or after Week 96, continuing treatment and completed treatment. Reasons for discontinuation are also included (eg, AE, lost to follow-up). The lower bounds of the on-treatment Week 48 and 96 visit windows are used to define the cuts on discontinuation (see [Section 8.4](#)).

Subject disposition from start to end of treatment is also summarized analogously by age randomization strata for each treatment regimen.

If  $\geq 5\%$  of treated subjects have as-randomized regimen different than as-treated regimen, then subject disposition from the start to end of treatment is summarized analogously by as-randomized treatment regimen for treated subjects.

Subject disposition from the start to end of long-term follow-up is based on the end of study subject status CRF, and is summarized for the Post-Year 1 Safety Cohort. The summary presents the number of subjects who entered long-term follow-up, did not complete long-term follow-up, completed long-term follow-up, continuing in long-term follow-up, and did not enter long-term follow-up. Reasons for not completing are also included. For subjects who entered long-term follow-up but indicated they were not continuing in the study on the end of treatment subject status CRF, the reason for not completing is set to the reason for not continuing.

### **7.3.4 Demographic and Other Baseline Characteristics**

Summaries are presented by as-treated treatment regimen for treated subjects unless specified otherwise. Summaries identify the number and percent of subjects with not reported (i.e., missing) measurements, unless specified otherwise.

If  $\geq 5\%$  of treated subjects have as-randomized regimen different than as-treated regimen, then demographics and baseline disease HBV characteristics are summarized analogously by as-randomized treatment regimen for treated subjects.

Demographic and other baseline characteristics are summarized by treatment regimen and overall for treated subjects:

- Demographics: age (years), age randomization strata ( $\geq 2$  to  $\leq 6$ ,  $> 6$  to  $\leq 12$ ,  $> 12$  to  $< 18$  years), gender, race, ethnicity, geographic region (Asia, Europe, North America, South America), country
- HBV disease characteristics: HBV DNA ( $\log_{10}$  IU/mL), Hepatitis B Surface Antigen (positive, negative, indeterminate), Hepatitis B E Antigen (positive, negative, indeterminate), Hepatitis B E Antibody (positive, negative, indeterminate), HBV genotype (e.g., A, B, C, D, E, indeterminate), INR, albumin (g/dL), ALT (U/L), ALT categories ( $\leq 2 \times$  ULN,  $> 2 \times$  ULN), total bilirubin (mg/dL), creatinine (mg/dL), glomerular filtration rate ( $< 50$ ,  $50 - 75$ ,  $> 75$  mL/min/1.73 m^2) estimated with Schwartz's formula, route of transmission (mother-to-

- child transmission; household/close contact exposure; transfusion; sexual contact; IV drug use; other)
- Physical measurements: height (cm), height for age Z score (HAZ), height for age percentile (HAP), weight (kg), weight for age Z score (WAZ), weight for age percentile (WAP), body mass index (BMI;  $\text{kg}/\text{m}^2$ ), BMI for age Z score (BMIAZ), BMI for age percentile (BMIAP) (see [Section 7.6.7](#))
  - Laboratory tests (see [Section 7.6.6.1](#))
    - Hematology by toxicity grade (ie, normal, Grade 1, 2, 3, 4)
    - Liver function tests by toxicity grade
    - Pancreatic enzymes by toxicity grade
    - Renal function tests by toxicity grade
    - Electrolytes (low and high) by toxicity grade
    - Glucose categories regardless of fasting status
  - Medical history by body system
  - Prior medications, defined as non-study medications taken before the first dose of study therapy.

Demographics and baseline disease HBV characteristics are also summarized analogously for the following: Primary Cohort; All ETV Safety Cohort; by age randomization strata for each treatment regimen.

For the All ETV Safety Cohort, age and HBV disease characteristics are summarized at ETV baseline. Age at ETV baseline is defined as  $(\text{first dose date of active ETV} - \text{birth date} + 1)/365.25$ .

See [Sections 8.5](#) and [8.9](#) for additional conventions.

## 7.4 Extent of Exposure

Extent of exposure is presented by as-treated treatment regimen for treated subjects to support safety.

### 7.4.1 Study Therapy

Extent of exposure to study therapy is summarized for blinded therapy (ETV active or PBO), open-label ETV, active ETV (blinded active ETV or open-label ETV), and all therapy (blinded therapy or open-label ETV) by treatment regimen as follows:

- Time on therapy (weeks):  $(\text{last dose date of drug} - \text{first dose date of drug} + 1)/7$ .
- Cumulative dose: total amount (mg) of drug summed across dosing records.
- Average daily dose: cumulative dose divided by time on therapy.

Extent of exposure to study therapy is also summarized analogously for the following: Primary Cohort; All ETV Safety Cohort; by age randomization strata for each treatment regimen.

Time on study therapy is also described by a Kaplan-Meier plot and life table. Discontinuations from study therapy are considered events in this analysis, and are identified by subjects with non-missing last dose date of study therapy. For subjects who have not discontinued, time on study therapy is censored at the maximum of the last dose date of study drug (ETV blinded active or PBO, ETV open-label).

Time in long-term follow up is summarized by treatment regimen for long-term follow-up subjects in the Post-Year 1 Safety Cohort. Time in long-term follow-up (weeks) is defined as (last contact date - last dose date of study therapy)/7.

Time in off-treatment follow up is summarized by treatment regimen for off-treatment follow-up subjects in the Post-Year 1 Safety Cohort. Time in off-treatment follow-up (weeks) is defined as (minimum(last contact date, start date of alternative anti-HBV therapy - 1) - last dose date of study therapy)/7.

Dose interruptions of study therapy more than 3 days are summarized by treatment regimen. Reasons for interruption are also identified.

See [Section 8.9](#) for additional conventions.

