Duration of Study: 5 years, or until the last study subject treated with rescue open-label ETV for an extreme elevation of ALT due to acute exacerbation of CHB completes 48-weeks of off-treatment follow-up; whichever is later.

Number of Subjects per Group: Approximately 180 total [randomized 2:1 to ETV (120) and Placebo (60)]; the target enrollment will be 30 subjects for each age group, with a minimum requirement of 18 subjects.

Study Population: Male and female patients 2 to < 18 years of age with a history of chronic HBV infection (defined as HBsAg positive at the Screening visit and on at least one other occasion \geq 24 weeks prior). All subjects must be nucleos[t]ide naive (< 12 weeks of prior therapy with any nucleos[t]ide antiviral agent with activity against hepatitis B virus and no anti-HBV treatment within 24 weeks of screening); have detectable HBeAg AND no detectable anti-HBe antibodies; have active viral replication and biochemical evidence of active hepatitis with compensated liver function.

Investigational Product(s), Dose and Mode of Administration, Duration of Treatment with Investigational Product(s): ETV dosing at 0.015 mg/kg/day up to a maximum dose of 0.5 mg/day using oral solution or tablets. During the treatment period, ETV dosing will be for a maximum of 144 weeks. Placebo (reference therapy) dosing with oral solution or tablets will be for a maximum of 96 weeks. A subject who experiences an extreme elevation of ALT due to acute exacerbation of CHB may be provided with rescue open-label ETV for up to 96 consecutive weeks at investigator's discretion and after discussion and approval by the BMS Central Medical Monitor. Rescue open-label ETV will be limited to those subjects who do not have access to acceptable alternative anti-HBV therapy.

Study Assessments and Primary Endpoints:

To test the study hypothesis, the primary endpoint of the analysis will be the proportion of subjects who achieve the composite of: 1) HBV DNA < 50 IU/mL (approximately 300 copies/mL) using the Roche COBAS[®] TaqMan HBV Test for use with the High Pure System (HPS) assay; and 2) HBeAg seroconversion (undetectable HBeAg AND detectable anti-HBe antibodies) at Week 48.

Key Secondary Endpoints:

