### 6.2 Treatment Regimens

Treatment regimens are described in Protocol Section 5.1 as ETV treated subjects (ETV) given a starting dose of 0.015 mg/kg up to a maximum dose of 0.5 mg and PBO subjects.

Treatment regimens are defined as follows:

- As-randomized refers to the treatment regimen assigned at randomization. Accrual and efficacy results are presented as-randomized.
- As-treated refers to the actual treatment regimen received. Subjects who receive the incorrect study therapy for the entire period of treatment are grouped according to the treatment regimen associated with the incorrect study therapy. Otherwise, subjects are grouped according to their randomized treatment regimen. Subjects who never receive study therapy have missing as-treated treatment regimen. Results for subject disposition, demographics, baseline characteristics, safety, and PK parameters are presented as-treated. Furthermore, important safety events that occur while a subject is on an incorrect treatment regimen are specifically discussed in the text of the Clinical Study Report.

If a subject receives at least 1 dose of drug in the randomized regimen, then the as-randomized treatment regimen is equal to the as-treated treatment regimen. If  $\geq 5\%$  of treated subjects have as-randomized regimen different than as-treated regimen, summaries are presented by both treatment regimens for select endpoints (see [Section 7](#)).

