## 8.10 Collapsed AEs and Exposure-Adjusted Incidence Rates

In order to account for AEs with multiple occurrences in the same subject, AE records are collapsed for each subject and preferred term when:

- Records have the same onset date.
- The onset date of an event record is either the same day or 1 day later than the resolution date of a preceding event record (contiguous events).
- The onset date of an event record is after the onset date and prior to or on the resolution date of a preceding event record (overlapping events).

The collapsed record contains the earliest onset date (and time, if collected); latest resolution date (and time, if collected); highest intensity in the following order (highest to lowest: very severe, severe, moderate, or mild); AE type of SAE, if ever reported as a SAE, AE otherwise; latest causality, as determined by the last modification time stamp (highest causality in the following order [highest to lowest: related, not related], if records contain the same last modification time stamp with different causalities); treatment required of yes, if ever required; highest action taken in the following order (highest to lowest: drug discontinued, drug interrupted, dose reduced, dose increased, none); latest reported term, as determined by the last modification timestamp.

Incidence rates per 100 person-years of exposure (IR/100 P-Y) are defined as event count \* 100 / person-years of exposure (see [Section 7.6.5](#)). Exposure is defined as time on study therapy (see [Section 7.4.1](#)), plus 5 days for subjects who discontinued study therapy to account for on-treatment safety reporting.

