### On-Treatment Protocol Deviations

Protocol deviations during the on-treatment period are as follows:

- Incorrect study therapy received: subjects randomized to active ETV who received PBO or the incorrect active dose; subjects randomized to PBO who received blinded active ETV. Subjects who received the incorrect study therapy during the entire treatment period are further identified.

- Blinded therapy received after not seroconverting at Week 48 (defined as receiving blinded therapy after 54 weeks and not seroconverting at Week 48 based on NC = M)
- Open-label ETV received after seroconverting at Week 48 without seroreversion (defined as receiving open-label ETV after 54 weeks, seroconverting at Week 48 based on NC = M, and seroreverting after Week 48 based on NC = M)
- Average daily dose < 80% of target dose
- Treatment continued after positive pregnancy test (defined as not discontinuing study therapy or discontinuing study therapy > 2 weeks after positive pregnancy test)
- Treatment continued after positive HIV test (defined as not discontinuing study therapy or discontinuing study therapy > 2 weeks after positive HIV test)
- Prohibited concomitant medications (#)

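### As written, the SAP's average daily dose divides milligrams by weeks, so a literal derivation is seven times the daily dose and would largely disable the 80%-of-target deviation

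*SAP*

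**What the plan says.** SAP 7.4.1 (Study Therapy) sets out three linked definitions.

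- Time on therapy is expressed in weeks: the inclusive number of days from first to last dose, divided by 7.
- "Cumulative dose: total amount (mg) of drug summed across dosing records".
- "Average daily dose: cumulative dose divided by time on therapy".

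No factor of 7 appears in the third definition, and no unit is given beyond the word *daily*. The summaries are produced by treatment regimen and repeated for the Primary Cohort, the All ETV Safety Cohort and the age randomization strata.

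SAP Appendix 1, under On-Treatment Protocol Deviations, lists "Average daily dose < 80% of target dose". It does not define the target dose there and does not refer back to 7.4.1. The protocol synopsis gives the dose per day: "ETV dosing at 0.015 mg/kg/day up to a maximum dose of 0.5 mg/day using oral solution or tablets". SAP 6.2 describes the active regimen as "given a starting dose of 0.015 mg/kg up to a maximum dose of 0.5 mg".

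**The concern.** Milligrams divided by weeks is a weekly amount. The target dose in this trial is a daily amount. If a programmer takes the 7.4.1 variables as defined, the row labelled as a daily dose is inflated, and the Appendix 1 rule compares a weekly figure with a daily one.

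At stake is whether under-dosing is visible. SAP 7.2 describes relevant deviations as those that could affect how the results are interpreted, and SAP 7.4 presents exposure in support of safety. The 80% rule is the only quantitative threshold on overall dose taken in the Appendix 1 list. A rule that misses a child on half the intended dose does not do that job.

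**Working it through.** The documents state no average-daily-dose value, so there is no figure of the plan's own to reproduce. The check is one of units.

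**Inputs**

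- *D* = days from first to last dose, inclusive. Time on therapy = *D*/7 weeks (SAP 7.4.1).
- *C* = cumulative dose in mg (SAP 7.4.1).
- *T* = target dose in mg/day (protocol synopsis and Table 5.3).
- *f* = fraction of the target dose taken, as captured in the dosing records, so *C* = *f* × *T* × *D*.

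**Formulas**

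- Literal SAP value: *C*/(*D*/7) = 7 × *f* × *T*, in mg per week.
- Daily value: *C*/*D* = *f* × *T*, in mg per day.
- Ratio: exactly 7, independent of *T* and *D*.
- Literal flag: 7 × *f* × *T* < 0.80 × *T*, so *f* < 0.80/7 = 0.114.
- Flag with days as the denominator: *f* < 0.80.

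**Example: a 20 kg child treated for 48 weeks.** Table 5.3 gives 6.0 mL, and the solution is 0.05 mg/mL, so *T* = 0.30 mg/day. With *D* = 336, full intake gives *C* = 0.30 × 336 = 100.8 mg. The flag limit is 0.80 × 0.30 = 0.24 mg/day.

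| Intake | *C* (mg) | Literal value, *C*/48 | Literal, % of target | Flagged, literal | *C*/336 (mg/day) | Flagged, days |
|---|---|---|---|---|---|---|
| 100% | 100.8 | 2.10 | 700% | no | 0.300 | no |
| 80% | 80.64 | 1.68 | 560% | no | 0.240 | no |
| 79% | 79.63 | 1.659 | 553% | no | 0.237 | yes |
| 50% | 50.4 | 1.05 | 350% | no | 0.150 | yes |
| 20% | 20.16 | 0.42 | 140% | no | 0.060 | yes |
| 12% | 12.10 | 0.252 | 84% | no | 0.036 | yes |
| 11% | 11.09 | 0.231 | 77% | yes | 0.033 | yes |

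**Other doses and durations**

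- 10 kg child (3.0 mL, 0.15 mg/day), 48 weeks: 50.4/48 = 1.05 against 0.15.
- 0.5 mg/day, 48 weeks: 168/48 = 3.5 against 0.5.
- 0.5 mg/day, 96 weeks: 336/96 = 3.5 against 0.5.

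The ratio is 7 each time. Dividing by days restores the intended value: 168/336 = 0.5 mg/day, or 100% of target.

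**The case against.** The strongest reply is that the intent is plain. The quantity is called daily, and comparing it with a target dose makes sense only in matching units. SAP 8.10 also leaves conversions of the same duration unwritten: it says "Exposure is defined as time on study therapy", points to 7.4.1, adds 5 days and reports rates per 100 person-years. A fully adherent subject showing 3.5 mg/day against a 0.5 mg maximum would be noticed. Appendix 1 does not cite 7.4.1, so the link between the formula and the deviation is inferred.

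This shows what was meant, and it is why the consequence has to be stated conditionally. It does not correct the formula. The SAP writes its divisors elsewhere (365.25 for age in 7.3.4, 7 for visit weeks in 8.4). The Year 2 Safety Cohort in 6.3 refers to 7.4.1 and uses a limit of more than 54 weeks of study therapy, so the variable does operate in weeks.

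A reader might go further and infer any of the following. The documents support none of them.

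- *Under-dosing could not be seen at all.* Appendix 1 also lists receipt of an incorrect active dose, and 7.4.1 summarises interruptions of more than 3 days with reasons.
- *All exposure results would be wrong.* Time on therapy, cumulative dose, the Kaplan-Meier display and the follow-up times do not use the quotient.
- *Efficacy conclusions are at risk.* SAP 7.5 analyses treated subjects as randomized, and no population in 6.3 is defined by dose taken.
- *A mean in mg/day is uninformative because dose follows body weight.* Absolute dose is a legitimate safety summary, and 7.4.1 repeats it by age stratum. Preferring a percentage of target in the table is a matter of taste.

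**Conclusion.** The unit mismatch is real and certain from the text: the stated formula gives mg per week, seven times the daily dose. Its effect on results is conditional. It arises only if the weeks variable is used unconverted, and the deviation is affected only if it uses the 7.4.1 quantity. Under those two assumptions, the 80% rule misses every subject whose recorded intake lies between about 11.4% and 80% of target.

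The reach is narrow: one row of the exposure summaries and one listed deviation. The primary and key secondary tests, the adverse event incidence rates and the other dosing checks do not use average daily dose. Nothing in the documents shows that the error was carried into a result, so it should not be reported as having happened. It is a wrong formula, not just a missing detail, and worth correcting before the derivation is programmed.

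**What to change.** In SAP 7.4.1, define average daily dose (mg/day) as cumulative dose in mg divided by the inclusive number of days from first to last dose of the drug. Equivalently, divide by 7 × time on therapy in weeks.

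In Appendix 1, state that the 80% deviation uses this mg/day value. Define the target dose as the protocol-specified daily dose for the subject's recorded weight (protocol Table 5.3), taking account of any dose modification made under protocol 5.3.1, in the same unit.

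The cost is one corrected line, one added sentence and a small derivation. Weight is already recorded at treatment visits and the dosing records already exist, so no new data are needed and no efficacy analysis changes.
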